10.2 Appendix 2: Contraceptive Guidance and Collection of Pregnancy Information

Study specific contraception requirements for males and females of childbearing potential are outlined in Section 5.2 exclusion criteria 22 and 23).

Male and female subjects of childbearing potential must receive pregnancy prevention counseling and be advised of the risk to the fetus if they become pregnant or father a child during treatment and for 5 months after the last dose of protocol required therapies.

Additional medications given during the study may further alter the contraceptive requirements. These additional medications may require female subjects to use highly effective methods of contraception and/or for an increased length of time. The investigator must discuss these contraceptive changes with the subject.

Definitions

Females of Childbearing Potential

A woman is considered fertile following menarche and until becoming postmenopausal unless permanently sterile (see below).

If fertility is unclear (eg, amenorrhea in adolescents or athletes) and a menstrual cycle cannot be confirmed before first dose of investigational product, additional evaluation should be considered. For more details on the definitions, refer to Section 5.2.

Women in the following categories are not considered females of childbearing potential:

- 1. Premenarchal
- Premenopausal female with one of the following:
 - Documented hysterectomy.
 - Documented bilateral salpingectomy.
 - Documented bilateral oophorectomy.

NOTE: Documentation can come from the site personnel's review of the subject's medical records, medical examination, or medical history interview.

3. Postmenopausal female

A postmenopausal state is defined as no menses for 12 months without an alternative medical cause.

 A high follicle stimulating hormone (FSH) level in the postmenopausal range may be used to confirm a postmenopausal state in women not using hormonal contraception or hormonal replacement therapy (HRT). However, in the absence of 12 months of amenorrhea, a single FSH measurement > 40 IU/L is required.

Final 1.0 Date: 03 Jun 2021 Page **80** of **87**

Females on HRT and whose menopausal status is in doubt will be required to use
one of the non-estrogen hormonal effective contraception methods if they wish to
continue their HRT during the study. Otherwise, they must discontinue HRT to
allow confirmation of postmenopausal status before study enrollment.

Contraception Guidance

Female Subjects:

Female subjects of childbearing potential are eligible to participate if they agree to use one of the following acceptable effective method of contraception throughout the duration of the study and for 5 months after last dose of study drug. as described below:

- Combined (estrogen and progestogen containing) hormonal contraception associated with inhibition of ovulation (oral, intravaginal, or transdermal).
- Progestogen-only hormonal contraception (oral, injectable, implantable).
- Intrauterine device.
- Intrauterine hormonal-releasing system.
- Bilateral tubal ligation/occlusion.
- Vasectomized partner (provided that partner is the sole sexual partner of the female subject of childbearing potential and that the vasectomized partner has received medical assessment of the surgical success).
- Sexual abstinence (defined as refraining from heterosexual intercourse during the
 entire period of risk associated with the study treatments; the reliability of sexual
 abstinence must be evaluated in relation to the duration of the trial and the
 preferred and usual lifestyle of the subject).
- Double barrier method: the male uses a condom and the female may choose either a cap, diaphragm, or sponge with spermicide (a female condom is not an option due to the risk of tearing when both partners use a condom).

Male Subjects:

Male participants are not required to use birth control during treatment with ABP 501. However, female partner of the study male participant should be informed about the study and subject's participation.

Clinical Study Protocol: 20200497

Final 1.0 Date: 03 Jun 2021 Page **81** of **87**

Pregnancy Testing

 Female of childbearing potential should only be included after a confirmed menstrual period and a negative highly sensitive serum pregnancy test.

- Additional pregnancy testing should be performed at intervals as per the Schedule of Assessments (Table 1-1), and as required locally.
- Pregnancy testing will be performed whenever a menstrual cycle is missed or when pregnancy is otherwise suspected.
- Pregnancy testing, with a sensitivity of 5 mIU/mL will be performed.

Collection of Pregnancy Information:

Male Subjects With Partners Who Become Pregnant

• In the event a male subject's partner becomes pregnant during treatment, and for an additional 5 months after the last dose of investigational product, the information will be recorded on the Pregnancy Notification Form. The form must be submitted to Amgen or its designee within 24 hours of the center's awareness of the pregnancy (Note: Sites are not required to provide any information on the Pregnancy Notification Form that violates the country or regions local privacy laws).

Clinical Study Protocol: 20200497

Final 1.0 Date: 03 Jun 2021 Page **82** of **87**

 The investigator will attempt to obtain a signed authorization for release of pregnancy and infant health information directly from the pregnant female partner to obtain additional pregnancy information.

- After obtaining the female partner's signed authorization for release of pregnancy and infant health information, the investigator will collect pregnancy outcome and infant health information on the pregnant partner and her baby and complete the pregnancy questionnaires. This information will be forwarded to Amgen or its designee.
- Generally, infant follow-up will be conducted up to 12 months after the birth of the child (if applicable).
- Any termination of the pregnancy will be reported to Amgen or its designee regardless of fetal status (presence or absence of anomalies) or indication for procedure.

Female Subjects Who Become Pregnant

- The investigator will collect pregnancy information on any female subject who becomes pregnant while taking protocol required therapies through 5 months after the last dose of investigational product.
- Information will be recorded on the Pregnancy Notification Form. The form must be submitted to Amgen or its designee within 24 hours of learning of a subject's pregnancy (Note: Sites are not required to provide any information on the Pregnancy Notification Form that violates the country or regions local privacy laws).
- After obtaining the female subject's signed authorization for release of pregnancy and infant health information, the investigator will collect pregnancy and infant health information and complete the pregnancy questionnaire for any female subject who becomes pregnant while taking protocol required therapies through 5 months after the last dose of investigational product. This information will be forwarded to Amgen or its designee. Generally, infant follow-up will be conducted up to 12 months after the birth of the child (if applicable).
- Any termination of the pregnancy will be reported to Amgen or its designee regardless of fetal status (presence or absence of anomalies) or indication for procedure.

Clinical Study Protocol: 20200497

Final 1.0 Date: 03 Jun 2021 Page **83** of **87**

While pregnancy itself is not considered to be an adverse event or serious
adverse event, any pregnancy complication or report of a congenital anomaly or
developmental delay, fetal death, or suspected adverse reactions in the neonate
will be reported as an adverse event or serious adverse event. Note that an
elective termination with no information on a fetal congenital malformation or
maternal complication is generally not considered an adverse event, but still must
be reported to Amgen or its designee as a pregnancy exposure case.

- If the outcome of the pregnancy meets a criterion for immediate classification as a serious adverse event (eg. female subject experiences a spontaneous abortion, stillbirth, or neonatal death or there is a fetal or neonatal congenital anomaly) the investigator will report the event as a serious adverse event.
- Any serious adverse event occurring as a result of a poststudy pregnancy which is considered reasonably related to the study treatment by the investigator, will be reported to Amgen or its designee. While the investigator is not obligated to actively seek this information in former study subjects, he or she may learn of a serious adverse event through spontaneous reporting.
- Any female subject who becomes pregnant while participating will discontinue study treatment.

Collection of Lactation Information

- Investigator will collect lactation information on any female subject who breastfeeds while taking protocol required therapies through 5 months after the last dose of investigational product.
- Information will be recorded on the Lactation Notification Form and submitted to Amgen or its designee within 24 hours of the investigator's knowledge of event.
- Study treatment will be discontinued if female subject breastfeeds during the study as described in exclusion criterion 24 (Section 5.2).
- With the female subjects signed authorization for release of mother and infant health information, the investigator will collect mother and infant health information and complete the lactation questionnaire on any female subject who breastfeeds while taking protocol required therapies through 5 months after discontinuing protocol required therapies.

Final 1.0 Date: 03 Jun 2021 Page **84** of **87**

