- 5. Female subject (except if postmenopausal or surgically sterile, definitions outlined in Section 10.2): a negative serum pregnancy test during screening and a negative urine pregnancy test at baseline.
- 6. Subject or legally acceptable representative is capable of giving signed Institutional Review Board (IRB)/Independent Ethics Committee (IEC) informed consent.
- 7. Subject has no known history of latent or active tuberculosis. Subject must meet any 1 of the following 3 criteria:
 - Subject has a negative test for tuberculosis during screening, defined as either:
 - Negative purified protein derivative (PPD); < 5 mm of induration at
 48 hours to 72 hours after test is placed, or
 - Negative QuantiFERON®/T-spot® test.
 - Subject with a positive PPD test and a history of Bacillus Calmette Guerin (BCG) vaccination is allowed with a negative QuantiFERON®/T-spot® test.
 - Subject with a positive PPD test (without a history of BCG vaccination) or subject with a positive or indeterminate QuantiFERON®/T-spot® test is allowed if he/she has all of the following:
 - No symptoms per tuberculosis worksheet provided by the sponsor, Amgen Inc.
 - Documented history of adequate prophylaxis initiation prior to receiving investigational product in accordance with local recommendations.
 - No known exposure to a case of active tuberculosis after most recent prophylaxis.
 - No evidence of active tuberculosis on chest radiograph taken within 3 months prior to the first dose of investigational product and read by a qualified radiologist/specialist.

Final 1.0 Date: 03 Jun 2021 Page 27 of 87

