Clinical Chemistry	Blood urea nitrogen Potassium Total bilirubin Creatinine Sodium Total protein Albumin	Glucose (random) Alkaline phosphatase AST ALT gamma-glutamyl transferase
Routine Urinalysis	pH, specific gravity, glucose, bilirubin, blood, and protein	
Other Screening Tests	FSH and estradiol (as needed in non-females of childbearing potential only) at screening Serum hCG pregnancy test (as needed for females of childbearing potential) at screening Serology (HBsAg, HBcAb, HCV, and HIV) at screening TBa testing (including a TB worksheet and chest X-ray) at screening Urine pregnancy tests Creatinine clearance Immunology (ADA)	

ADA = antidrug antibody; ALT = alanine aminotransferase; AST = aspartate aminotransferase;

FSH = follicle-stimulating hormone; HBcAb = hepatitis B core antibody; HBsAg = hepatitis B surface antigen;

hCG = human chorionic gonadotropin; HCV = hepatitis C virus; RBC = red blood cell; TB = tuberculosis; WBC = white blood cell; QuantiFERON®/T-spot® or purified protein derivative testing.

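### Section 10.2 is most naturally read as letting one FSH value above 40 IU/L replace 12 months without menses, which removes the contraception undertaking for a woman with recent menses

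*Protocol*

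**What the plan says.** The Definitions part of protocol Section 10.2 sets a default: "A woman is considered fertile following menarche and until becoming postmenopausal unless permanently sterile". The third category of women not of childbearing potential is the postmenopausal female, for whom "A postmenopausal state is defined as no menses for 12 months without an alternative medical cause". The first bullet below says that a high FSH may confirm that state in women using neither hormonal contraception nor HRT. It then continues: "However, in the absence of 12 months of amenorrhea, a single FSH measurement > 40 IU/L is required".

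The next bullet begins "Females on HRT and whose menopausal status is in doubt will be required to use" a non-estrogen hormonal method if they stay on HRT. Otherwise they must stop HRT to "allow confirmation of postmenopausal status before study enrollment".

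Three other places depend on this definition:

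- Section 5.1, inclusion criterion 5, requires a negative serum test at screening and a negative urine test at baseline of each female subject, "except if postmenopausal or surgically sterile, definitions outlined in Section 10.2".
- Section 5.2, exclusion criterion 22, asks for effective contraception during the study and for 5 months after the last dose. It applies only to a female of childbearing potential who is sexually active with a male partner, and its footnote takes the definition from Section 10.2.
- Table 8-1 lists "FSH and estradiol (as needed in non-females of childbearing potential only) at screening" and "Serum hCG pregnancy test (as needed for females of childbearing potential) at screening".

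**The concern.** The FSH sentence speaks only to women who do not meet the 12-month definition, yet it stands under the heading for postmenopausal women. If 12 months were needed in every case, the sentence would do nothing. Its working effect is that a single value replaces the 12 months, with no repeat test and no minimum interval since the last menses.

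What is at stake is subject protection during exposure. A woman so classified leaves criterion 22, and also the pregnancy-prevention counseling in Section 10.2, which is addressed to subjects of childbearing potential. Enrollment is open from 18 to 75 years, so women near menopause can enter. Section 6.7 describes elimination of adalimumab as slow, over several months.

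**Working it through.** The plan has no figure of its own to reproduce. The check is mainly of text, followed by a short count of days and tests.

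**Text**

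1. Default: fertile until postmenopausal (Section 10.2).
2. Definition: 12 months without menses, with FSH as confirmation (Section 10.2).
3. FSH sentence: addressed to women without those 12 months; it asks for one value above 40 IU/L and nothing more.
4. Postmenopausal means not of childbearing potential (Section 10.2, category 3), so criterion 22 does not apply and criterion 5 no longer requires her two entry tests to be negative.
5. No other text settles the reading. Section 10.2 points to Section 5.2 for more detail on the definitions, and the footnote in Section 5.2 points back to Section 10.2. Table 8-1 provides FSH only for women already classed as not of childbearing potential, so it does not say how a woman enters that class.

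**Length of the missing undertaking** (a woman who completes dosing)

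- The week 28 target is day 190 (SAP Section 5.1), so 190 − 1 = 189 days from day 1.
- Five consecutive calendar months last 150 days (February to June, non-leap year) to 153 days (for example March to July).
- Nominal schedule: 189 + 150 = 339 to 189 + 153 = 342 days. Dividing by 365/12 = 30.4 gives 11.1 to 11.2 months.
- With the ±3 day week 28 window: 186 + 150 = 336 to 192 + 153 = 345 days.
- Table 1-1 also allows a dose to be delayed by up to 5 days for an infection or adverse event. The documents do not say whether this adds to the window; if it does, the upper end is 345 + 5 = 350 days.

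Roughly 11 months holds throughout.

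**Pregnancy tests that remain**

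- Table 1-1 lists 1 serum test (screening) and 6 urine tests (baseline, weeks 6, 12, 20, 28 and 32), 7 in all, with no childbearing restriction. Only the serum test is qualified, in Table 8-1.
- The last scheduled test is at week 32, target day 218, which is 218 − 190 = 28 days after the last dose. That leaves 150 − 28 = 122 to 153 − 28 = 125 days of the 5 months with no scheduled test. The tests detect pregnancy; they do not replace contraception.

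**Number of women affected:** not derivable. Neither document gives a split by sex or age.

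**The case against.** The best defence is that there is no error. The sentence opens with a contrasting word and follows the general rule, so it can be a deliberate second route: 12 months of history, or FSH above 40 IU/L. On the strictly literal reading, a required FSH value is only a necessary condition; the 12-month definition still governs and nobody leaves criterion 22. Nor do the documents say that one such value is clinically inadequate.

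Much of this stands. A reader might infer that Section 10.2 contradicts itself, but a rule followed by an exception is not a contradiction. A reader might also set the stricter HRT bullet against the FSH bullet as an inconsistency. The text does not support that either: FSH confirmation is confined to women not on HRT, which explains the different treatment.

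The defence does not remove the point. If the exception is intended, it sets aside the protocol's own default without asking for any time since the last menses. If it is not intended, two sites can classify the same woman differently. The point rests on that default and makes no claim about how reliable FSH is.

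The defence is also right that simply reclassifying these women causes a difficulty. The Pregnancy Testing part of Section 10.2 says that a female of childbearing potential should be included only after a confirmed menstrual period. A woman with, say, 9 months of amenorrhea may be unable to show one, so the fix has to deal with this.

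**Conclusion.** The point holds as a low-severity safety gap. It concerns a woman with menses in the past year who uses neither hormonal contraception nor HRT, is sexually active with a male partner, and has one FSH value above 40 IU/L. She could take part without a contraception undertaking for roughly 11 months. This assumes that the site reads the FSH sentence as an exception and that she receives the week 28 dose.

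A reader might infer that such women go untested or that a pregnant woman could properly be enrolled. The documents do not support this. Criterion 24 excludes any female subject who is pregnant or planning pregnancy, Table 1-1 lists the tests, Section 10.2 requires a test after a missed cycle or on suspicion, and pregnancy leads to discontinuation of study treatment. What is missing is the undertaking against an unplanned pregnancy. The number of women is unknown and may be zero. The PK and efficacy analyses and the sample size are untouched.

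**What to change.** At the next amendment, replace the FSH sentence in Section 10.2 with:

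> Without 12 months of amenorrhea, a single FSH value is not sufficient to establish a postmenopausal state; the subject is treated as a female of childbearing potential for criteria 5 and 22. For such a subject who cannot show a recent menstrual period, the negative serum pregnancy test at screening and negative urine test at baseline satisfy the inclusion condition under Pregnancy Testing.

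At the end of the HRT bullet add:

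> If postmenopausal status cannot be confirmed before enrollment, the subject is treated as a female of childbearing potential.

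Criterion 22 and Table 8-1 stay as they are, and no procedure is added to Table 1-1. The cost is that a few women must agree to a listed contraception method (abstinence is on the list) or are not eligible. Stopping HRT to confirm menopausal status would then help only a woman whose history already shows the 12 months.

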10.3 Appendix 3: Static Physician's Global Assessment Scale

Below is the sPGA scale that will be used in this study.

Score	Category	Category Description
0	Clear	Plaque elevation = 0 (no elevation over normal skin).
		Scaling = 0 (no scale).
		Erythema = no evidence, hyperpigmentation may be present.
1	Almost Clear	Plaque elevation = ± (possible but difficult to ascertain whether there is a slight elevation above normal skin).
		Scaling = ± (surface dryness with some white coloration).
		Erythema = light red coloration.
2	Mild	Plaque elevation = slight (slight but definite elevation, typically edges are indistinct or sloped).
		Scaling =fine (fine scale partially or mostly covering lesions).
		Erythema = light red coloration.
3	Moderate	Plaque elevation = moderate (moderate elevation with rough or sloped edges).
		Scaling = coarser (coarse scale covering most or all of the lesions).
		Erythema = moderate (definite red coloration).
4	Severe	Plaque elevation = marked (marked elevation typically with hard or sharp edges).
		Scaling = coarse (coarse, non-tenacious scale predominates covering most or all of the lesions).
		Erythema = severe (very bright red coloration).
5	Very Severe	Plaque elevation = very marked (very marked elevation typically with hard sharp edges).
		Scaling = very coarse (coarse, thick tenacious scale over most of the lesions, rough surface).
		Erythema = very severe (extreme red coloration, dusky to deep red coloration).

Clinical Study Protocol: 20200497

Final 1.0 Date: 03 Jun 2021 Page **85** of **87**

10.4 Appendix 4: Abbreviations and Trademarks

ADA antidrug antibody

ALT alanine aminotransferase **AST** aspartate aminotransferase

ANCOVA analysis of covariance

AUC_{tau} area under the curve from time 0 over the dosing interval

Bacillus Calmette Guerin **BCG**

BPCI Biologic Price Competition and Innovation Act

BSA body surface area

CHO Chinese hamster ovary CL confidence interval

 C_{max} maximum concentration COVID-19 coronavirus disease 2019 **CRA** clinical research associate

CRF case report form

CRO contract research organization

CSR clinical study report

CTCAE Common Terminology Criteria for Adverse Events

 C_{trough} trough concentration

DMC Data Monitoring Committee

DNA deoxyribonucleic acid

eCRF electronic case report form

EDC electronic data capture

EOS end of study EU European Union

FSH follicle stimulating hormone

GCP Good Clinical Practice GMR geometric mean ratio

HBsAg hepatitis B surface antigen

hCG human chorionic gonadotropin

HCV hepatitis C virus

HRT hormonal replacement therapy

ICF informed consent form

ICH International Council for Harmonization of Technical Requirements for

Pharmaceuticals for Human Use

IEC Independent Ethics Committee

IL Interleukin

Clinical Study Protocol: 20200497 Final 1.0 Date: 03 Jun 2021

Page **86** of **87**

IMP investigational medicinal product

IP investigational product
IRB Institutional Review Board

IV Intravenous

IXRS Interactive Web/Voice Response System
NIMP non-investigational medicinal product
PASI Psoriasis Area and Severity Index
PGA Physician's Global Assessment
PIN personal identification number

PK pharmacokinetic(s)

PPD purified protein derivative

Ps plaque psoriasis
RA rheumatoid arthritis

RBC red blood cell

sPGA static Physician's Global Assessment

TB Tuberculosis

TNFRSF tumor necrosis factor receptor superfamily

QA quality assurance QTL quality tolerance limit

Q2W every 2 weeks RBC red blood cell

SAP statistical analysis plan

SARS-CoV-2 severe acute respiratory syndrome coronavirus 2

SC Subcutaneous

 $\begin{array}{ll} \text{SmPC} & \text{Summary of Product Characteristics} \\ t_{\text{max}} & \text{time of maximum concentration} \end{array}$

TNFα tumor necrosis factor alpha

TMF trial Master File
US United States

USPI United States Prescribing Information

WBC white blood cell

Clinical Study Protocol: 20200497

Final 1.0 Date: 03 Jun 2021 Page **87** of **87**

11 References

Amgen Inc. ABP 501 – Investigator's Brochure Version 6.1, 2021.

